**Teaching Academic Success Skills to Students with Autism Spectrum Disorders in the
Clinical Setting**

Study Protocol and Statistical Analysis Plan

Clinical Trials.gov Identifier: NCT03606343

September 22, 2020

STUDY PROTOCOL

PURPOSE OF STUDY:

The goal of the study is to develop an academic EF intervention, *Achieving/Academic Independence in Middle School (AIMS)*, for high functioning (i.e., IQ score ≥ 80) middle-school youth with ASD and EF deficits. The primary aim is to: Examine the feasibility and acceptability of AIMS in a series of open trials (n=21) including the feasibility of: 1) implementing the measurement protocol, 2) operationalizing intervention delivery, 3) assessing both trained and untrained areas of functioning, 4) assessing whether improvements in academic EF skills (*proposed mechanism of treatment*) are related to functional educational outcomes (e.g., homework behaviors, grades), and 5) exploring the data for potential treatment moderators (e.g., gender, severity). It is hypothesized that AIMS will be feasible, acceptable (attendance, satisfaction), and will result in improved academic EF skills associated with reduced academic impairment and homework problems.

STUDY DESIGN:

Open Trial: To document proof of concept and gather sufficient preliminary data for a future RCT, 3 cohorts of youth with ASD (n=21) will be recruited (three groups will be recruited to participate in the group intervention; the maximum group size for this intervention is 7 based on the level of individualized attention needed during the intervention). A research assistant will observe all sessions and complete treatment fidelity checklists to monitor adherence. Sessions will also be videotaped for later use (e.g., training, fidelity coding). The primary teacher will complete organization and time management checklists weekly. We do not anticipate making major changes to the intervention during the open trials; however, as needed the intervention manual may be refined to be clearer. Parent(s) and their teen will attend 7 intervention sessions offered 1 week apart at CCHMC. Session content will include psychoeducation about the academic EFs in ASD and will be taught strategies and skills targeting these deficits, including using a behavioral contract (i.e., Agreement), organization skills (e.g., homework system, binder organization, etc.), time management skills (e.g., planner), problem solving skills, and study skills (e.g., flash cards). We will also be doing midweek check-ins with parents during the intervention to increase accountability and coach parents as needed.

Post Assessment and Exit Interviews: The primary measures collected will be treatment fidelity and academic EF skills acquisition, although other measures will be collected to pilot these measures and methods for collection and to gather information about whether they capture gains made by families. Parents and youth with ASD will also be surveyed regarding their experience of the intervention and whether they understood intervention materials in exit interviews.

Consultation with Experts: A webinar will be scheduled to process the information obtained during the open trial, including the feedback from the parents, and youth obtained in the exit interviews, the fidelity ratings, the utility and feasibility of the proposed measures.

Finalize Intervention Manual: A finalized draft of the manual will be developed including sections on troubleshooting, treatment rationale, strategies for specific skills, case examples, and

guidance for establishing and maintaining effective relationships with participants⁶⁸ will be incorporated. Finalized graphics and storyboards will be selected and scripts revised for the animated clips depicting important content.

Participants

Youth with ASD: The target population is high functioning middle school youth (6, 7, and 8th graders ages 10 to 14) who have an educational label of Autism (e.g., school referred) and/or meet diagnostic criteria for ASD (e.g., clinic referred). In cases where it may need to be clarified (e.g., youth attends a specialized school for ASD, or the child is in an intermediate school), we will confirm that youth transition between teachers for core academic subjects. For research purposes, the diagnosis of all youth will be confirmed using the ADOS-2. All participants with ASD will present with EF problems based on the parent or teacher rated BRIEF-2 T-Score >60 on the Planning, Organization, or Monitor subscales.

An IQ score ≥ 80 will be required in order to select a high functioning population that will be most likely to profit from the intervention and are more likely to be in the mainstreamed educational environment or be eligible for mainstreaming.

Youth in middle school (typical age range 10 to 14) attending public or private middle/junior high schools will be recruited. Youth receiving pullout special education services for the majority of the day will be excluded because services required for those individuals would exceed that which AIMS could address. Additionally, those who receive significant support in the classroom (e.g., one-on-one aide for the whole school day) may not benefit from the intervention given its focus on promoting independence and initiative; this will be verified by reviewing the IEP.

Both sexes will be represented although more males than females (4:1 ratio) are anticipated given prevalence data for ASD⁶⁹.

Parents/Caregivers of Youth with ASD: Since parents/caregivers will be critically involved in implementing and reinforcing the intervention components, their input will be invaluable. Parents will be the primary caregiver of a child with high functioning ASD, English-speaking, and be willing and able to attend the intervention sessions.

Expert Consultants: An expert panel of consultants with expertise in academic issues facing youth with ASD and with developing and implementing school-based interventions will provide feedback on the final manual.

Measures: Measures collected will include information on family background, and measures assessing eligibility, EF, academic functioning, self-determination, parent-child relationship and satisfaction. Also see Table 1.

Participant Demographics & Eligibility:

Family Demographic/Developmental History: Includes family status, parent occupation, education, medical and developmental history, school history (including special education placements) completed by parents.

*Autism Diagnostic Observation Schedule, 2nd Edition (ADOS-2)*⁷⁰ is the “gold standard” clinician-administered assessment that will examine social interaction, language and communication, and restricted and repetitive behaviors and interests. All youth will be administered Module 3 of the ADOS-2 to confirm ASD diagnosis. Note that if an ADOS-2 has

been administered within the past two years by staff at CCHMC, parents will be asked to sign a release of information form and the results from that assessment will be obtained.

*Kaufman Brief Intelligence Tests-2 (K-BIT)*⁷¹: The K-BIT is a culturally-sensitive standardized assessment that estimates verbal and non-verbal and overall intelligence. This test has good reliability and validity and will be administered to confirm that the participant has an IQ ≥ 80 . Note that if a K-BIT has been administered within the past year for other research studies at CCHMC, parents will be asked to sign a release of information form and the results from that assessment will be obtained.

Executive Functioning

*Behavior Rating Inventory of Executive Function (BRIEF)*⁷³: Parents and teachers will complete the BRIEF assessing EF behaviors in the home and school environments.

*Children’s Organizational Skills Scale (COSS)*⁷⁴: Parents, teens, and teachers will complete the COSS assessing multiple facets of a child’s organizational skills.

Academic Functioning

*Subtests of the Woodcock Johnson Tests of Achievement III (WJ)*⁷⁶: Reading Comprehension (#9,#17), Basic Writing Cluster (#7,# 16), Math Reasoning Cluster (#10, #18), and the Academic Knowledge subtest (# 19) will be administered to assess academic achievement in student participants.

*Homework Problems Checklist (HPC)*⁷⁷: The HPC is a parent-report instrument that is commonly used as a screening tool for and outcome measure of homework problems.

*Classroom Performance Survey (CPS)*⁷⁸: The CPS, completed by teachers, is a measure of academic impairment specifically designed for secondary school youth. A shorter variant of this scale will be completed by teachers on a weekly basis while the child is attending the intervention.

*Academic Performance Rating Scale (APRS)*⁷⁹: The APRS is a 19-item scale that is completed by the teacher that measures how well the child is performing academically in the classroom.

Parent-Youth Relationship

*Parenting Relationship Questionnaire (PRQ)*⁸⁰. The PRQ is a parent-report instrument reporting on how parents feel about their children and the task of parenting. Subscales include Communication, Involvement, Satisfaction with School, Parenting Confidence, Relational Frustration, Attachment, and Discipline Practices. Lower T-scores indicate greater severity of relationship problems. This measure is included to assess whether parents report improvements in communication, satisfaction with school, increased confidence, and decreased frustration.

Table 1. Measures	Rater	Time	Eligibility	Pre	AIMS	Post	Domain
Autism Diagnostic Observation Schedule	Y	60	X				
Kaufman Brief Intelligence Test – Second Ed. (KBIT-2)	Y	20	X				
Behavior Rating Inventory of Executive Function Second Edition (BRIEF-2)	P, T	10	X			X	EF
Children’s Organizational Skills Scale (COSS)	P, T, Y	10		X		X	EF
Woodcock Johnson (WJ-III) Achievement Subtests	Y	30		X		X	A
Homework Problems Checklist (HPC)	P	5		X		X	A
Classroom Performance Survey (CPS)	T	10		X		X	A
Academic Performance Rating System (APRS)	T	10		X		X	A

Parenting Relationship Questionnaire (PRQ)	P	10-15		X		X	PY
--	---	-------	--	---	--	---	----

Y = Youth, P = Parent, T = Teacher, EF = academic executive functioning skill, A = academic outcome, PY=Parent-Youth relationship, I = Independence/Initiative, S = Satisfaction

Recruitment and Informed Consent

The investigative team has considerable experiencing with recruiting and retaining youth with ASD in intervention studies and recruitment difficulties are not anticipated. The team has well-established contacts with public and private school systems in Cincinnati and surrounding areas, and notices will be placed in schools to alert teachers and parents about this research opportunity. Clinicians and physicians at the Kelly O’Leary Center (TKOC) for Autism, the Division of Developmental Behavioral Pediatrics, and the Division of Psychiatry at Cincinnati Children’s Hospital Medical Center’s (CCHMC) will also be notified about this opportunity. Participants with ASD will also be recruited from local schools, including those specializing in ASD, as well as from the TKOC.

At TKOC, students will be identified through a variety of resources including (1) an existing database of children and adolescents who were previously assessed and diagnosed with an ASD at TKOC; (2) [name] existing research database of 150 youth with ASD who have participated in her previous studies; (3) an existing research database of ~60 youth with ASD who have participated in studies through the CCHMC Psychiatry Department; (4) treatment referrals from clinicians at TKOC and community providers. Currently, there are 178 youth between the ages of 10 to 14 years, which is the typical age of middle schoolers, who were evaluated or received treatment at TKOC in 2017 and could be recruited for the current research study; additionally, there are 94 individuals in this age range on the waitlist for services at TKOC that could also be approached. Families may be sent a letter indicating that they were identified because of having been seen previously at TKOC along with a “do not contact” postcard. Families not returning the postcards will be called by research staff to share more about the study and invite participation.

At schools, Student Services Directors, Special Educators, school mental health professionals, and/or teachers will be approached to identify high functioning middle school students with ASD who might be interested in participating. These individuals will be provided with a recruitment letter and flyer to distribute to parents of these youth. Students with an Individualized Education Program (IEP) that includes items related to EF (e.g., organization challenges), or whom teachers and/or school MHPs consider as having significant challenges in these domains will be of particular interest.

Participants may be recruited using IRB-approved materials including advertising and/or print, electronic, social and digital media, news/broadcast, face-to-face marketing and flyers at Cincinnati Children’s and in the community. Some of these recruitment materials will direct potential participants to a REDCap e-screener page where potential participants will be directed to provide contact information so that study staff may contact the participants to inform them about the study.

An initial eligibility screen will be conducted by telephone which will include asking parents to give verbal permission for us to contact the teacher to complete the BRIEF-2. Eligible families will be invited to an in-person screening visit at CCHMC. At the in person screening visit, the consent form and assent form, which are written in a language that is understandable to parents and teens, will be reviewed in detail. The consent form will also clarify that their data will be shared with other researchers via the National Database for Autism Research (NDAR) without exposing personally identifiable information. Upon conclusion of the review, the project

coordinator will ask if the parent and child are still interested in the study and if they are willing to sign the consent/assent forms— one will be provided for the family to keep for their records and one to sign for the study. We may consent the families electronically and send them an electronic copy of the consent/assent forms via REDCap. After signing the consent/assent forms, the baseline assessment battery will commence. This will include the a) ADOS-2⁷⁰ to assess ASD symptoms, the Stanford-Binet 5th Edition⁷² to confirm IQ, and the BRIEF-2 to confirm EF difficulties. For those youth who meet criteria, additional measures will be administered either at the screening visit or at a second visit depending on the families' wishes and fatigue level, assessing the outcomes of interest (e.g., Homework Problems Checklist, academic testing). We will also be asking the parents to bring a copy of their child's school IEP in order to determine if they fit criteria of being in a mainstream classroom for majority of the day without too much support from school staff.

Teachers are also participants in this study as they complete ratings of academic functioning that are critical to the study aims. Thus, engaging and retaining school personnel throughout the study will be important. The PIs will provide an overview of the study to teachers and provide an opportunity to ask questions as needed. The importance of teacher participation will be emphasized as crucial to accomplishing the aims of the study. In addition, teachers will be compensated for their time and effort in completing ratings.

STATISTICAL ANALYSIS PLAN

Descriptive statistics will summarize attendance, satisfaction (AIQ), fidelity, drop-out rates, exit interview data to assess feasibility and acceptability. Within group (pre-test, post-test) mixed factorial ANCOVAs controlling for pre-test scores will test for the presence of improvements. It is hypothesized that youth with ASD will demonstrate improved academic EF skills (BRIEF-2, COSS, HPC). The primary analytic focus will be on evaluating whether the observed effect sizes across outcomes warrant continued study of AIMS as a treatment strategy. A moderate (i.e., Cohen's $d = .5$ ⁸¹) effect size for academic EF measures will be evidence of significant improvement. We will explore whether AIMS improves academic (WJ, CPS, APRS), and parent-child relationship (PRQ) outcomes between pre- and post- assessments. Correlations between changes in academic EF skills and changes in the other outcomes measures will also be computed to explore whether changes in academic EF skills are related to functional academic outcomes, as these are the primary target and proposed mechanism of treatment.

Exploratory Analyses: We will also explore potential moderators such as sex, IQ, ASD and EF severity, and socioeconomic status qualitatively and with non-parametric statistics given the lack of power.

References

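### The SAP treats the homework checklist as an EF measure although Table 1 codes it as an academic outcome, so the hypothesised EF-to-homework link is not tested as written; grades have no listed measure

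*Combined protocol and SAP*

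**What the plan says.** Purpose of Study sets as its fourth feasibility aim the assessment of whether improvement in academic EF skills, the proposed mechanism, is related to "functional educational outcomes (e.g., homework behaviors, grades". The hypothesis that follows expects "improved academic EF skills associated with reduced academic impairment and homework problems".

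The Measures section announces "measures assessing eligibility, EF, academic functioning, self-determination, parent-child relationship and satisfaction". It places the HPC under Academic Functioning and describes it as "commonly used as a screening tool for and outcome measure of homework problems". Table 1 gives the HPC domain code A, which the legend defines as an academic outcome distinct from code EF, and schedules it at Pre and Post. Recruitment and Informed Consent also uses the HPC as an example of an outcome of interest.

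The SAP groups it differently: "It is hypothesized that youth with ASD will demonstrate improved academic EF skills (BRIEF-2, COSS, HPC". Its academic set is then stated without the HPC: "We will explore whether AIMS improves academic (WJ, CPS, APRS), and parent-child relationship (PRQ) outcomes between pre- and post- assessments". The mechanism analysis correlates change in academic EF skills with change in the remaining outcome measures, which that sentence does not list. A Cohen's d of .5 on the academic EF measures is taken as evidence of significant improvement.

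No grade, grade-point average or report-card item appears in the measures text, in Table 1 or in the SAP. The nearest item is the APRS, a 19-item teacher scale that "measures how well the child is performing academically in the classroom".

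**The concern.** The mechanism question needs two separate sets of measures: EF skills on one side and functional outcomes on the other. Homework stands on the functional side in the aim, the hypothesis, the measures text and Table 1, but on the EF side in the SAP. An analyst who follows the SAP will not compute the association that the hypothesis names.

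There is a second consequence. With the HPC in the EF set, a fall in parent-reported homework problems can be counted as evidence that the mechanism moved, even if neither the BRIEF-2 nor the COSS changed. The trial is meant to inform a later RCT, so confusing the mechanism with the outcome would affect what that RCT is built on.

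Grades are a smaller matter. The aim offers them as an example of an outcome to be related to EF gains, but the plan gives no way to obtain or analyse them. As written, the trial could not report whether collecting grades is feasible.

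**Working it through.** The plan states no figure to reproduce, and no sample size, power or alpha enters. The check sets the sections side by side and then counts pairs.

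| Place | Homework (HPC) | Grades |
|---|---|---|
| Purpose of Study, aim 4 | functional outcome (example) | functional outcome (example) |
| Purpose of Study, hypothesis | outcome side of the association | not mentioned |
| Measures text | Academic Functioning | no measure |
| Table 1 | code A, Pre and Post | no row |
| SAP, improvement hypothesis | academic EF skill | not mentioned |
| SAP, academic set | absent | absent |

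**Pairs in the mechanism correlation.** Number of pairs = EF instruments × academic instruments. Each instrument is counted once, although the BRIEF-2 and COSS have more than one rater.

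- SAP grouping: EF = BRIEF-2, COSS, HPC; academic = WJ, CPS, APRS. Pairs = 3 × 3 = 9. Pairs with homework as the outcome: 0. The HPC enters 1 × 3 = 3 of the 9, but as the EF skill.
- Table 1 grouping: EF = BRIEF-2, COSS; academic = WJ, HPC, CPS, APRS. Pairs = 2 × 4 = 8. Pairs with homework as the outcome: 2 × 1 = 2 (BRIEF-2 with HPC, COSS with HPC).
- Grades: 0 under either grouping.

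Adding the parenting scale (PRQ) to the outcome side gives 3 × 4 = 12 and 2 × 5 = 10 pairs. The homework counts stay at 0 and 2.

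**The d = .5 criterion.** The SAP does not say how many EF measures must reach .5. Suppose, as an assumption, that the BRIEF-2 and COSS both show d = 0:

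- If one measure suffices, an HPC effect of .5 meets the criterion alone.
- If the mean of the three is used, the HPC effect would have to be 3 × .5 = 1.5, since (0 + 0 + 1.5)/3 = .5.
- If all three must reach .5, the HPC cannot meet it alone.

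So whether a homework gain by itself counts as EF improvement depends on a rule that the SAP does not give. The wording allows it.

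**The case against.** A reader might infer that neither homework nor grades is tested as an outcome at all. The documents do not support that for homework. The HPC is collected at Pre and Post, is named in the SAP's improvement hypothesis, falls under the pre-post ANCOVAs and is judged against d = .5.

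A reader might also infer that grades will never be collected. The text shows only that no measure is listed. The listing is visibly incomplete: the Table 1 legend defines domains I and S that have no rows, self-determination and satisfaction are announced without a described instrument, and the AIQ appears only in the SAP. Absence from the list is therefore not proof, though it leaves grades unspecified.

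A third tempting inference is that grades would be the outcome best protected from rater expectancy. Nothing in the documents shows this. Grades are ordinarily assigned by teachers, and teachers here are study participants who complete ratings and may receive an overview of the study. The WJ, a test given to the youth, is already collected.

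The aim's two outcomes are introduced as examples, and the rest of the functional side survives: the CPS, described as a measure of academic impairment, covers that half of the hypothesis, and the WJ and APRS remain. This weakens the point about grades, which the hypothesis does not repeat. It does not answer the point about homework, because the hypothesis names homework problems without presenting them as an example.

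Finally, the HPC's place on the EF side rests on one parenthesis in the SAP, and the correlation sentence lists no instruments. That is true, but the SAP's academic set also omits the HPC, and the SAP is the text an analyst would follow.

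**Conclusion.** The point holds as an internal inconsistency of limited size. The HPC has two incompatible roles, and under the SAP's role the EF-to-homework association stated in the hypothesis is not among the planned correlations (0 of 9 instrument pairs, against 2 of 8 under Table 1). Whether a homework gain alone can satisfy the EF criterion is left open by the missing decision rule. Grades are named in aim 4 but have no listed source, time point or analysis.

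This rests on reading the SAP's parentheses as its definition of the EF and academic sets, and the remaining outcome measures in the correlation as those outside the EF set. It does not mean that homework goes unanalysed or that the mechanism analysis is empty. The correction is worth making because it is nearly free.

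**What to change.** **Homework.** In the SAP, state the academic outcomes as WJ, HPC, CPS and APRS. Define the EF set as BRIEF-2 and COSS, and use that set both for the d = .5 criterion and for the mechanism correlations. State that change in each EF measure will be correlated with change in the HPC. Table 1 and the measures text then need no edit. This costs a few words and no new data, and HPC pre-post change should stay in the analysis as an academic outcome. One caution for interpretation: Table 1 has the HPC rated by parents, who also rate the BRIEF-2 and COSS, so results using the teacher and youth versions should be shown alongside those using the parent versions.

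**Grades.** Choose one of two options:

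- Ask parents for the report cards covering the periods before and after AIMS, and add mean core-subject grade to Table 1 (Pre, Post, domain A) and to the SAP as an exploratory academic outcome. Parents are already asked to bring the IEP, so the burden is one further type of document. The downside is that grading periods and scales may not align across schools or with the 7 weekly sessions, and with n = 21 the correlation would be descriptive only.
- Delete grades from aim 4, which is a wording change and avoids implying a result that the plan cannot deliver.

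### In this one-arm pre/post study, the ANCOVA with the pre-test as covariate does not specify a valid unconditional test of mean change; a paired test does

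*Combined protocol and SAP*

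**What the plan says.** The Purpose section describes a single-group feasibility study: "Examine the feasibility and acceptability of AIMS in a series of open trials (n=21"). Under Study Design, "3 cohorts of youth with ASD (n=21) will be recruited", and one aim is to "gather sufficient preliminary data for a future RCT". Table 1 shows one assessment before and one after the intervention for each outcome. No comparison arm is described.

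The Statistical Analysis Plan states the hypothesis ("It is hypothesized that youth with ASD will demonstrate improved academic EF skills (BRIEF-2, COSS, HPC") and the test ("Within group (pre-test, post-test) mixed factorial ANCOVAs controlling for pre-test scores will test for the presence of improvements"). It names no between-subject factor. It does not say whether the covariate is centred, whether it interacts with time, or which error term is used. No alpha is given. The SAP then says: "The primary analytic focus will be on evaluating whether the observed effect sizes across outcomes warrant continued study of AIMS as a treatment strategy".

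**The concern.** Adjusting for baseline is useful when arms are compared, because it sharpens the between-arm contrast. Here there are no arms, and the quantity of interest is the mean of post minus pre. The baseline is already half of that difference. Entering it again as a covariate can change the standard error, change the hypothesis tested, or do nothing, depending on how the model is set up.

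This is the only test the SAP names for the improvement hypothesis. At stake is a p-value or confidence interval that is somewhat too favourable, or that answers a different question, in results meant to inform a later randomised trial.

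**Working it through.** **Inputs from the documents.** One arm, one pre and one post assessment, n=21. The sample size reproduces as 3 cohorts × the maximum group size of 7 = 21. No alpha, power, SD or correlation is stated, so no other figure can be reproduced.

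**Assumptions.** Two-sided 5% level, bivariate normal scores, no true mean change, independent children, no dropout, pre-post correlation r = 0.5, 0.7 or 0.8, and equal pre and post SD σ unless stated. Rejection rates are from 200,000 simulated trials per main setting (60,000 for the second score scale below, 100,000 for the check with fixed baselines). Let D = post − pre.

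**Reading 1: D regressed on the mean-centred pre-test (a time-by-covariate term is present).**
- The intercept equals the mean change.
- True variance of mean D: 2σ²(1−r)/n. Variance the model uses: σ²(1−r²)/n.
- SE ratio = sqrt[(1−r²)/(2(1−r))] = sqrt((1+r)/2) = 0.866, 0.922, 0.949.
- Large-sample rejection rate 2[1 − Φ(1.96 × ratio)] = 9.0%, 7.1%, 6.3%. Simulated at n=21: 8.7%, 6.8%, 6.1%.
- Conditional on fixed baselines: 5.0%, 4.9%, 5.0%. The shortfall is the sampling variance of the baseline mean, which the model leaves out.
- With k = post SD / pre SD, the ratio is sqrt[k²(1−r²)/(1+k²−2rk)]. It never exceeds 1, because the denominator minus the numerator is (1−rk)². For k = 0.8 rejection is 13.0%, 11.4%, 11.0%; for k = 1.2 it is 6.6%, 5.2%, 4.9%, so the excess can vanish.
- With the three cohorts as an effect-coded factor: 8.7%, 6.8%, 6.1%, unchanged. With 17 completers (assumed): 8.5%, 6.8%, 6.1%.

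**Reading 2: the same model, covariate uncentred.** The intercept estimates change at a pre-test score of 0. With no true mean change its expectation is (1−r)μ. For an illustrative T-score mean μ = 68 that is 0.5×68 = 34, 0.3×68 = 20.4 and 0.2×68 = 13.6 points. With SD 8, rejection is 66%, 42%, 29%, almost all toward higher scores. With mean 20 and SD 10 on an arbitrary scale it is 58%, 36%, 25%.

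**Reading 3: post-test as the only outcome, adjusted for pre-test.** With no second arm there is no contrast left to test. The model gives an adjusted post-test mean, not a change.

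**Reading 4: split-plot ANCOVA, pre-test as a participant-level covariate, no time-by-pre-test term.** The covariate is constant within a participant and cancels from the within-participant difference. The time F is therefore the squared paired t on n−1 = 20 df. On one simulated data set both gave t = −0.3103, p = 0.7595.

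This identity needs the participant error stratum. In a random-intercept REML fit with time and pre-test, the expected between-participant mean square is σ²(1−r²)/2. The within-participant one is σ²(1−r), which is larger whenever r < 1. The intercept variance is then estimated as zero in about 92%, 80%, 69% of trials and the errors pool. Rejection is about 7%, 6%, 6%.

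| Test of no mean change (nominal 5%) | r=0.5 | r=0.7 | r=0.8 |
|---|---|---|---|
| Centred covariate | 8.7% | 6.8% | 6.1% |
| Uncentred covariate (mean 68, SD 8) | 66% | 42% | 29% |
| Split-plot, participant stratum kept | 5.0% | 5.0% | 5.0% |
| Paired t | 5.1% | 4.9% | 4.9% |

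**The case against.** The best defence is that the words mixed factorial fit Reading 4, which is a valid unconditional test. That stands. A reader might infer that the planned ANCOVA is invalid however it is read; the SAP wording does not support this, since one natural reading is exactly the paired test. The defence shows, however, that the covariate is idle in the good case. It also depends on a setup that the SAP does not state.

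Second, effect sizes are the main focus, no alpha is set, and a d from raw mean change is untouched. That also stands and limits the severity.

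Third, the centred test is correct conditional on the observed baselines. True, but the SAP does not say that conditional inference is intended, and planning a later trial calls for inference to the wider population.

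Fourth, a reader might take the 66% figure as the chance of a false claim of benefit. The documents do not support this. It needs an uncentred covariate with an interaction and an assumed mean and SD, and the rejections point to higher scores. On BRIEF-2, where entry requires a high score, higher is worse.

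**Conclusion.** The concern holds as a gap in specification with a modest consequence. The sentence does not fix a valid unconditional test of mean change. Two plausible setups mislead, a third does not test change, and the one that works is the paired t-test.

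Under the centred reading, type I error is about 9%, 7% or 6% at r = 0.5, 0.7 or 0.8 with equal SDs and n=21. It is higher if the post SD is smaller, and near 5% if the post SD is somewhat larger. The correlations, SDs and 5% level are assumptions, as the documents give none. Impact is minor to moderate. It should be fixed because the correction is nearly free.

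**What to change.** Replace the sentence with: *Pre-to-post change on each outcome will be tested with a paired t-test (n−1 degrees of freedom), without the pre-test as covariate, and reported as mean change with 95% CI.*

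A mixed model with time as the fixed effect, a random participant intercept and Satterthwaite or Kenward-Roger degrees of freedom is equivalent on complete data. The t reference matters: with a normal reference, type I error is about 6.5% at n=21. If conditional inference is wanted, the SAP should say so and centre the covariate.

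**Cost.** No new data. Nominal power for a change of half a score SD (4 points at SD 8) is 59%, 80%, 93% at r = 0.5, 0.7, 0.8, against 69%, 84%, 94% with the centred ANCOVA. Part of that gap is the latter's inflated type I error.

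**Limits to state alongside.**
- The paired test does not remove regression to the mean on BRIEF-2. Entry requires a "parent or teacher rated BRIEF-2 T-Score >60 on the Planning, Organization, or Monitor subscales", and Table 1 marks BRIEF-2 at eligibility and post only, so the eligibility rating is the baseline. If the analysed score were itself truncated at 60, the paired t would reject in 10%, 8%, 7% for an assumed mean of 68 and SD of 8. Entry on any of three subscales from either rater may weaken this.
- Nor does it allow for clustering within the three groups. If 5% of the variance of change lay between groups, it would reject in about 8%.

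The standardiser for the d = .5 criterion is also unstated; that is a separate point.
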